6. STUDY PROCEDURES

6.1 Study Procedures

Antenatal diagnosis of TGA followed by a referral to the Fetal Cardiac Program at SickKids is typically made during mid-gestation. Fetal echocardiography including a late-gestational MRI is routinely used in the assessment of all prenatally diagnosed TGA.

The initial echocardiogram allows differentiating between simple vs complex form of TGA and determining whether or not a patient fulfills eligibility criteria to potentially participate in the study. The physician will explain the possibility of MH in the last trimester that as a diagnostic test may help with the management of future patients with the same condition. If the patient is interested in hearing more details about MH, more information will be provided to help families decide whether they would like to participate in the study. This will allow coordination of echocardiograms and MRI studies on the same day, whenever possible.

Mothers with fetal TGA are routinely seen at SickKids for a final fetal echocardiogram in late gestation (≥ 34 gestational weeks). The final exam includes detailed re-evaluation of all cardiac structures including blood flows across the atrial septum, AV and semilunar valves, arterial duct, pulmonary and cerebral blood flows, among other. Following the exam, perinatal management recommendations are made and discussed with the family. This typically includes the

recommendation of 1) delivery at Mount Sinai Hospital, 2) initiation of IV prostaglandin at birth, and 3) referral to SickKids critical cardiac care unit for early neonatal care that may include preoperative BAS. Whether a mother elects to participate or not in this study, the baseline echocardiogram and perinatal management will not be affected by the maternal decision.

The following are study-related additional procedures, if a mother who fulfills all inclusion and none of the exclusion criteria consents in writing to participate in this study:

- 1) A fetal echocardiogram during acute MH
- 2) A fetal MRI during acute MH

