6.1.2 Fetal Echocardiography

All fetal echocardiograms will be performed with standard GE Voluson E-10 or Philips IU 22 ultrasound systems within the Echo Lab facility or the Cardiac Diagnostics & Interventions Unit (CDIU) at SickKids. Fetal echocardiography poses no known risks to the mother and her fetus.

At the final visit, the mother will initially undergo a baseline fetal echocardiogram that will include the assessment of left and right ventricular outflow tract (peak flow, velocity time integral (VTI), heart rate, aortic and pulmonary valve diameters), the arterial duct (systolic and end-diastolic flow, forward/reverse flow ratio, VTI, diameter), branch pulmonary artery (peak flow, pulsatility index calculated as peak systolic velocity – end-diastolic velocity/mean velocity), pulmonary veins (VTI), atrial septum (FO diameter, atrial shunt direction and velocities, atrial septal excursion), mid cerebral artery (peak, VTI), as well as ventricular dimensions (diameter in 4CV; volumes by 3/4D). These findings will be digitally recorded and all measurements will be made offline by the responsible cardiologist to abbreviate the duration of the exam. The percent changes in flow VTIs, percent changes in flow PIs and DA forward/reverse flow ratios will be calculated using the echocardiography data.

Immediately following the baseline echocardiogram, maternal oxygen will be administered in the same room via a sterile face mask to reach about 65-70% of oxygen and delivered at a rate of 10 to 15L/minute. After a 5 minute-period to allow fetal steady-state oxygenation, the same echocardiographic variables as above will be recorded during continuous maternal O₂ supplementation, which is expected to take maximally 30 minutes or less. During the exam, the fetal wellbeing will be continuously monitored by fetal echocardiography, which allows us to continuously see the baby's movements and heart function. Oxygen supplementation will be

stopped once the above imaging variables have been obtained or after a maximum of 30 minutes (5 minutes initiation + 25 minutes echocardiogram) if the test cannot be completed within this time frame. No further research related measurements will be obtained once the MH has terminated.

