6.1.3 Fetal MRI

We routinely perform late-gestational MRI for fetal TGA before birth to examine fetal hemodynamics and the brain. Fetal MRI poses no known risks to the mother and her fetus. Baseline and MH MRI will be performed as usual with a clinical 1.5T MR system in the CDIU. No sedation or invasive techniques will be required to perform MRIs on pregnant women. The MRI study will take a maximum of 90 minutes including MH study, which is expected to take maximally 45 minutes. The subjects will be fitted with their usual supply of oxygen via a face mask during MRI. The same amount of O₂ at the same flow rate will be administered as described above.

As with all our fetal MRI studies, a standard multichannel body surface coil will be placed over the maternal abdomen and imaging performed for a maximum of one hour. MR flow assessments will be acquired according to our previously published technique to examine the distribution of blood flow across the fetal circulation (15). The PC MR acquisitions will be analyzed using a commercial software (Q-flow, Medis) and the oximetry measurements will be analyzed using a region of interest placed over the central 50% of the vessel diameter on the T2 map, according to our previously published techniques (15,16). The imaging protocol has been detailed in previous publications and includes T1 and T2 weighted imaging, diffusion tensor imaging, MR spectroscopy and brain volumetry (15,17). MR oximetry will be recorded in the ascending aorta (AAo), superior vena cava (SVC), descending thoracic aorta (DAo), umbilical vein (UV) and main pulmonary artery (PA). Oxygen content at baseline and during MH will be measured offline at the level of the LV/MPA, RV/AAo and DAo. Blood flow quantifications (baseline and MH; cine-phase contrast) will be made in the AAo, DAo, main and branch PAs, SVC, IVC, UV and DA. Other variables will include estimated hematocrit (HCT), fluximetry, brain volumetry (baseline; 3D steady state), cDO₂ and cVO₂ (baseline and MH; T2 mapping) to measure oxygen consumption. Oxygen supplementation will be stopped once the above imaging variables have been obtained or after a maximum of 45 minutes (5 minutes initiation + 40 minutes MRI) if the test cannot be completed within this time frame. No further research related measurements will be obtained once the MH has terminated.

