8. STATISTICS

This is an observational cohort study to test whether acute MH is a useful diagnostic test for fetal TGA. This requires confirmation of the study concept that among TGA fetuses there will be specific hemodynamic and structural characteristics and responses that will be associated with neonatal compromise shortly after birth. Neonatal compromise is defined as any of these outcomes: pre-op/BAS mortality; minimal pre-BAS pH ≤ 7.1 , SaO₂ $\leq 40\%$, PaO₂ ≤ 25 mmHg, maximal serum lactate ≥ 10 mmol; and/or PPHN (combined pre-operative reverse differential cyanosis $\geq 30\%$ and/or postoperative RVp $\geq 75\%$ systemic ≥ 48 h post-surgery or $\geq 50\%$ at postoperative discharge). Twenty-two (31%) of 70 consecutive newborns born at Mount Sinai Hospital for fetal TGA/IVS fulfilled at least one of the outcomes ([name] et al. AEPC 2016). PPHT affects 1-3% of children with TGA. Based on these data we would expect about 35 cases without severe neonatal compromise, 15 cases with neonatal compromise and 1 case with PPHT.

Simple descriptive statistics will be adequate for this small feasibility and safety study. Data obtained from this study will further help to describe the possible ranges in hemodynamic findings at baseline and during MH in a larger cohort of TGA patients and in comparison with our previous data. The comparison between pre and post MH variables will be analysed using the Brand Altman's plot. Receiver operating statistics will be used to test the diagnostic value of MH.

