9. STUDY ADMINISTRATION

9.1 Data Collection, Management and Confidentiality

Data will be collected by the study investigators using the above described sources and their personal usernames and passwords. Study investigators will be responsible for the data management and the accuracy of the records. Only the study team will have access to the

database. Data will be recorded on a Microsoft Excel spreadsheet and will be maintained in a locked digital file on the hospital's secure server. Data will be backed up on the hospital's secure server. Any research information obtained about the patient in this study will be kept confidential. A patient will not be identified by name, only by unique study ID number. The patient's name or any identifying information will not appear in any reports published as a result of this study. All identifying information will be kept behind 2 security measures or as per equivalent institutional policy, under the supervision of the study Principal Investigator and will not be transferred outside of the hospital. Relevant study records will be archived for 25 years following completion of the study, as per the requirements of Health Canada's Food & Drug Act, Part C Division 5. Once the study is complete and the final report has been published, the records will be retained and destroyed in accordance with The Hospital for Sick Children Record Retention and Destruction policy. All information collected in this study will be kept confidential in accordance with institutional policies on subject privacy and PHIPA. Investigators will not use data for any purpose other than conducting the study.

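### Nothing requires the research readings under maternal hyperoxygenation (MH) to be finished before birth or read masked to outcome, so the ROC estimate is open to review bias

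*Combined protocol and SAP*

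**What the plan says.** Section 6.1.2 (Fetal Echocardiography) has the images recorded digitally and states that "all measurements will be made offline by the responsible cardiologist to abbreviate the duration of the exam". The sentence follows the list of baseline variables. For the oxygen phase the section adds that "the same echocardiographic variables as above will be recorded during continuous maternal O₂ supplementation", and percent changes in VTI and pulsatility index are calculated from the echo data.

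Section 6.1.3 (Fetal MRI) states: "Oxygen content at baseline and during MH will be measured offline at the level of the LV/MPA, RV/AAo and DAo". It does not say who reads.

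Section 9.1 (Data Collection, Management and Confidentiality) states: "Data will be collected by the study investigators using the above described sources". Database access is limited to the study team, with no separation inside it between imaging and outcome data.

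Section 8 (Statistics) states: "Receiver operating statistics will be used to test the diagnostic value of MH". It names no ROC input variable and no cut-off.

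No section gives a reading deadline, a lock before delivery, or masking of the image reader to neonatal outcome.

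**The concern.** The index test here is the fetal response to oxygen as measured from stored images. The reference standard is neonatal compromise, which becomes known within days of birth. If images are read or re-read once that outcome is known, borderline readings can drift toward the pattern the reader expects, and the AUC rises for reasons unrelated to the test.

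Three features make this more than a formality.

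- Section 2.4 sets out the expected imaging pattern for each of four clinical scenarios, so a reader who knows the outcome also knows which pattern to look for.
- That section's one numeric marker of pulmonary response, a fall of at least 10% in branch PA pulsatility index, is formed from two readings, so a small change in either can move a borderline fetus across it.
- Section 6.3 includes fields that rest on judgement: septal excursion, shunt description, and ductal flow restriction as yes or no.

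At stake is the answer to the question in Sections 1 and 8: whether MH is a useful diagnostic test.

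**Working it through.** **1. Does any provision already close the gap?**

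- Sections 6.1.2 and 6.1.3 both say: "No further research related measurements will be obtained once the MH has terminated". Offline reading takes place after the images are taken, so this can only limit acquisition.
- Section 6.1 says: "Following the exam, perinatal management recommendations are made and discussed with the family". This makes a clinical baseline read before birth likely. It does not reach the MH readings, because the same section says perinatal management does not depend on participation. No clinical need forces the MH values to be ready by delivery.
- Section 6.1.1 assigns study numbers for data entry. That protects privacy and does not mask an image reader.
- Section 6.1.1 also has consent taken by someone outside the patient's care. No similar separation is made for reading.

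None of these closes the gap.

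**2. The plan's own case split.** Inputs from Section 8: 22 of 70 historic newborns with compromise, and N = 50.

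- With compromise: 50 × 22/70 = 15.7 (plan: 15).
- Without compromise: 50 × 48/70 = 34.3 (plan: 35).

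The plan's figures reproduce to within one case. PPHN is already part of the compromise definition, so the plan's 15 versus 35 is used below. The documents give no target AUC, alpha or power to reproduce.

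**3. Sampling error of the AUC (Hanley-McNeil), n1 = 15, n0 = 35.**

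SE² = [A(1−A) + (n1−1)(Q1−A²) + (n0−1)(Q2−A²)] / (n1·n0), where Q1 = A/(2−A) and Q2 = 2A²/(1+A).

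- A = 0.70: Q1 = 0.538, Q2 = 0.576. SE² = (0.210 + 14 × 0.0485 + 34 × 0.0865)/525 = 0.0073, so SE = 0.085 and the 95% interval is 0.53 to 0.87.
- A = 0.50: SE = 0.090, 95% interval 0.32 to 0.68.

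**4. Illustrative bias (binormal, equal variance).** Let s be an outcome-driven shift in the mean reading of the compromised group, in SD units. The values of s are assumptions; the documents offer none.

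d = √2·Φ⁻¹(AUC), and shifted AUC = Φ((d + s)/√2).

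For AUC 0.70, d = 1.414 × 0.524 = 0.742. With s = 0.25: Φ(0.992/1.414) = Φ(0.701) = 0.758.

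| True AUC | s = 0.1 | s = 0.25 | s = 0.5 |
|---|---|---|---|
| 0.50 | 0.528 | 0.570 | 0.638 |
| 0.70 | 0.724 | 0.758 | 0.810 |

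At 0.70 with s = 0.25 the gain is 0.058, or 0.058/0.085 = 0.68 of one standard error.

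**5. The same point by counting pairs.** The AUC averages over 15 × 35 = 525 pairs. Suppose one compromised case is re-read so that it passes half of the uncompromised cases. That gains 17.5 pairs, or 17.5/525 = 0.033. Three such cases add 0.10. How many readings would move, and how far, is again assumed.

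**The case against.** A reader might infer that the protocol lets the readings be made at any time, that they will be made after birth, or that the reported AUC will be inflated. The documents support none of these. They are silent on timing, and the only reason given for offline reading is a shorter exam. That the MH echo is read offline is itself inferred from its having the same variables as baseline and from the percent changes, though this is the natural reading.

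Other points on the plan's side also stand.

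- Section 2.2 describes the final echo and MRI as standard care for predicting neonatal risk, so baseline values are less exposed.
- MRI region-of-interest placement is fixed in Section 6.1.3 at the central half of the vessel diameter, flow is analysed with named software, and most echo variables are numeric. These leave less room for discretion, and the documents do not say that the judgement-based fields enter the ROC analysis.
- Compromise in Section 8 is death or numeric thresholds, and Section 9.1 does not say that the image reader also abstracts outcomes. The exposure is on the index-test side.
- The study is a pilot with mainly descriptive statistics and no AUC threshold to cross, and a plausible shift is smaller than the sampling error.

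The last point does not remove the concern. Sampling error is visible in a confidence interval; review bias is not, and it acts in one direction. The study may be small, but ROC is its chosen analysis for the diagnostic question.

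**Conclusion.** The point holds as an open risk. The exposure lies mainly in the MH readings, the percent changes derived from them, and the research-only MRI quantities; it is lower for baseline readings. Nothing shows that bias will occur, and its size cannot be known from the documents. Under an assumed shift of 0.25 SD and a binormal model, a true AUC of 0.70 would appear as about 0.76 and one of 0.50 as about 0.57. Both lie well inside the sampling error at the plan's expected 15 versus 35 cases, so neither could be recognised in the results. Once outcomes are known, the only remedy is masked re-reading. The protocol should be changed, because the protection is cheap and is best put in place before outcomes accrue.

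**What to change.** State in Sections 6.1.2 and 6.1.3 that all baseline and MH research measurements, echo and MRI, are completed, date-stamped and locked in the database before delivery, and that any later change is logged.

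A rule is needed for babies born before the lock. The final exam is at 34 weeks or later with no upper limit, the MRI may fall on another day, and no interval from exam to delivery is given. Keep such cases and flag them. Where possible, have them read by an existing team member who does not know the outcome. Add to Section 8 a sensitivity analysis that repeats the ROC analysis without the flagged cases.

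The cost is protocol wording, a lock date in the database, a reading deadline for the cardiologist and the MRI reader, and one small extra analysis. Sample size, study procedures and clinical care do not change, and no additional reader has to be recruited.

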2.4 Study Rationale

To examine the baseline fetal hemodynamics as well as the response to acute MH as an added diagnostic test, we will combine various fetal echocardiographic and MR imaging tools. The prenatal findings will then be compared to the neonatal presentation.

We postulate that conditions that predispose newborns to acute neonatal compromise will be detectable and distinguishable prior to birth by echocardiography, MRI, or by combining the findings of both exams. We expect to encounter the following 4 clinical scenarios:

- 1) *TGA/IVS with unrestricted atrial shunting before and after birth:* we expect fetal baseline differences in LV/RV O₂ content and DAo/AAo O₂ content related to unrestricted right-left atrial shunting. MH is expected to further increase the differences in LV/RV O₂ content and DAo/AAo O₂ content, which leads to an increase pulmonary blood flow, LV preload and LV stroke volume due to O₂-mediated vasodilation of the pulmonary vasculature. As a confirmation of pulmonary vaso-reactivity to O₂, the branch PA pulsatility index will decrease by $\geq 10\%$ and this will coincide with lower peak systolic flow and reversal of end-diastolic flow across the DA.
- 2) *TGA/IVS with in-utero RAS:* In the absence of intracardiac shunting, RV/LV and DAo/AAo O₂ content will be equal at baseline and with MH and no significant effect on pulmonary flow will be observed.
- 3) *TGA/IVS with postnatal RAS:* RV/LV and DAo/AAo O₂ content will differ at baseline when the FO is still patent. With MH-induced functional closure of the FO by the septal flap, the RV load and AAo O₂ content will preferentially increase to reach an equal or higher oxygen content and saturation when compared with the LV, MPA, DA and DAo.
- 4) *TGA with PPHN:* supplementary maternal O₂ will not affect fetal pulmonary blood flow and PA pulsatility.

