6.3 Collected Patient Data

A) Prenatal Echocardiography

- Date of exam (dd/mmm/yyyy)
- Gestational age at exam (weeks/days)
- Estimated fetal weight (g)
- MPA valve diameter
- Aortic valve diameter

Imaging variables at baseline and with MH:

Atrial septal morphology (2D; 4D) and foramen flow (color; 4D flow)

FO diameter

Septal excursion

Shunt description

Branch PA flow (mid-portion)

peak flow

VTI

PI (peak systolic velocity – end-diastolic velocity/mean velocity)

PV Doppler flow:

VTI

MPA:

VTI

Heart rate

LCO

AAo:

VTI

Heart rate

RCO

DA flow (color and Doppler):

minimal diameter

reversed end-diastolic flow: yes – no

systolic peak flow

forward-reverse flow ratio

flow restriction: yes - no
MCA Doppler flow
peak flow
VTI
PI
UA Doppler flow
Peak flow
VTI
PI

RV and LV (4D): volumes

B) Fetal MRI

- Date of exam
- Gestational age at exam (weeks+days)
- Fetal weight estimation (g)
- Fetal weight Z-score
- Fetal weight percentile
- Brain volumetry (mL) (baseline; 3D steady state)
- Placenta volumetry (mL)
- Estimated HCT
- UV
- DAo
- Ventricle (specify R or L)
- Imaging variables at baseline and with MH

Cardiovascular oximetry (SatO₂):

LV

MPA

RV

AAo

DAo

UV

SVC

Fluximetry (ml/min/m²):

AAo

DA

Main PA

RPA

LPA

SVC

IVC

UV

DA

Brain (ml/min/m²):

cDO₂
cVO₂
Fetus (ml/min/m²)

DO₂
VO₂

Placenta Volumetry
T2 star

Patient Safety during MH

- Adverse events

C) Postnatal Outcomes

- Date of birth (dd/mmm/yyyy)
- Delivery place
- Gestational age at birth
- Weight at birth
- Placental weight at birth
- APGAR score (1 and 5 minutes)
- PaO₂ and SpO₂
- Age at CCU admission
- Neonatal interventions: stat BAS, oxygen, intubation/ventilation, ECMO, other
- Neonatal PGE: yes – no; time of start
- Neonatal BAS: yes – no; age at procedure
- Pre-op/pre-BAS: hemoglobin; minimal pH; minimal preductal PaO₂; peak lactate
- Pre-BAS compromise (defined as minimal pre-BAS pH \leq 7.1, SaO₂ \leq 40%, PaO₂ \leq 25 mmHg, maximal serum lactate \geq 10 mmol): yes - no
- Pre-BAS echo: ASD and VSD size, shunting, and gradients
- Persistent pulmonary arterial hypertension (defined as combined pre-operative reverse differential cyanosis \geq 30% and/or postoperative RVp \geq 75% systemic \geq 48h post-surgery and/or \geq 50% at postoperative discharge): yes – no
- Pre-op complications: organ failure; NEC, cerebro-vascular injury; death
 - o Date of event
 - o Age at event
- Date of surgery
- Age at surgery
- Type of surgical repair: ASO; VSD closure, other

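### The ductal forward/reverse flow ratio has no value when reverse flow is zero, so analyses of it may run on a subset selected by the oxygen response

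*Combined protocol and SAP*

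**What the plan says.** Section 6.1.2 lists the baseline ductal measurements as "the arterial duct (systolic and end-diastolic flow, forward/reverse flow ratio, VTI, diameter" and states that "the same echocardiographic variables as above will be recorded during continuous maternal" oxygen. For the derived variables it says "percent changes in flow PIs and DA forward/reverse flow ratios will be calculated using the echocardiography data". The sentence does not define the components of the ratio, and it is unclear whether the percent change applies to the ratio or only to the VTIs and PIs.

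Section 6.3 lists "forward-reverse flow ratio" among the ductal items collected at baseline and with MH, next to a separate item "reversed end-diastolic flow: yes – no". It lists neither the forward and reverse components nor a ductal VTI.

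Section 2.4, scenario 1, expects a fall in branch pulmonary artery pulsatility in responders and adds that "this will coincide with lower peak systolic flow and reversal of end-diastolic flow across the DA". Scenarios 2 and 4 expect no effect on pulmonary flow and do not mention the duct.

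Section 6.1.3 adds an MRI measure of ductal flow: "Blood flow quantifications (baseline and MH; cine-phase contrast) will be made in the AAo, DAo, main and branch PAs, SVC, IVC, UV and DA". Section 8 plans a Bland–Altman plot of values before and with MH, and ROC statistics for the diagnostic value of MH. It names no ROC index variable and gives no rule for undefined values.

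**The concern.** Ductal shunting is part of the primary objective (4.1), and this ratio is the only derived echo index in 6.1.2 that is specific to the duct. The yes/no item shows that the plan expects some fetuses to have no end-diastolic reversal. If their ductal flow is wholly forward, the ratio does not exist. If reversal is part of the response to oxygen, the existence of the ratio is itself informative about response, and dropping undefined values discards that information and selects the sample.

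The loss can run both ways. A responder who reverses only during MH has a ratio with MH but none at baseline, so the paired change is undefined. A non-responder who never reverses has no ratio at either time. A blank field in 6.3 would also be ambiguous. It could mean no reverse flow or a measurement not obtained, and 6.1.2 allows the examination to end incomplete at the time limit.

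**Working it through.** **The plan's own figure.** Section 8 gives 22 of 70 newborns with compromise and N = 50. 50 × 22/70 = 15.7 with and 50 × 48/70 = 34.3 without compromise. PPHT at 1–3% gives 0.5–1.5. The plan states about 15, 35 and 1, which agrees. The total of 51 fits PPHT being counted within the compromise definition. The documents give no figure for the ductal ratio or for how often ductal flow reverses.

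**Behaviour of the scale.** Let F be forward and R reverse flow (illustrative values, F = 10).

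| R | F/R | R/(F+R) |
|---|---|---|
| 2 | 5 | 0.167 |
| 1 | 10 | 0.091 |
| 0.1 | 100 | 0.010 |
| 0 | undefined | 0 |

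From R = 2 to 1 the ratio moves by 5 and the fraction by 0.076. From R = 1 to 0.1 the ratio moves by 90 and the fraction by 0.081. From R = 0.1 to 0 the ratio ceases to exist and the fraction moves by 0.010.

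The two scales can also order changes differently. Compare two illustrative fetuses whose reverse flow doubles:

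- Fetus A, F = 12, R from 0.2 to 0.4. Ratio 60 to 30, a change of −30. Fraction 0.2/12.2 = 1.6% to 0.4/12.4 = 3.2%, a change of +1.6 points.
- Fetus B, F = 10, R from 1 to 2. Ratio 10 to 5, a change of −5. Fraction 9.1% to 16.7%, a change of +7.6 points.

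The ratio calls A the larger change and the fraction calls B the larger. A percent change in the ratio is −50% in both. On a Bland–Altman plot of the ratio, a few fetuses like A would set the limits of agreement.

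**How many pairs exist.** A paired ratio needs reverse flow at both times, so the number of pairs is at most 50 × (share with reverse flow at baseline). That share is not given. At 0%, 20%, 60% and 100% the ceiling is 0, 10, 30 and 50. The documents do not narrow this range.

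**Effect on an ROC analysis with MH values.** Assume a share qc of the 15 compromised and qn = 10% of the 35 uncompromised have no reverse flow during MH. A complete-case analysis then keeps 15(1 − qc) cases and 35 × 0.9 = 31.5, about 32, non-cases. The Hanley–McNeil variance is

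SE² = [A(1 − A) + (n1 − 1)(Q1 − A²) + (n2 − 1)(Q2 − A²)]/(n1·n2), with Q1 = A/(2 − A) and Q2 = 2A²/(1 + A).

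At A = 0.80, Q1 = 0.667 and Q2 = 0.711. With all 50, SE² = (0.16 + 14 × 0.0267 + 34 × 0.0711)/525 = 0.00562, and 1.96 × SE = 0.147.

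| qc | cases kept | non-cases kept | 95% half-width | AUC of absent reverse flow alone |
|---|---|---|---|---|
| 25% | 11 | 32 | 0.169 | 0.575 |
| 50% | 8 | 32 | 0.196 | 0.70 |
| 75% | 4 | 32 | 0.271 | 0.825 |

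The last column is 0.5 + (qc − qn)/2. If the ratio had the same distribution in both groups among fetuses with reverse flow, the complete-case AUC would be 0.50. Keeping the others as the extreme rank would give the last column. That gap is the information discarded. If the shares were equal, for example 50% in both groups, absence of reverse flow would carry no information (AUC 0.50). The only cost would then be sample size: 8 and 18 kept, half-width 0.204.

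**The case against.** The strongest counter-argument is that the ratio is one measure among several. Ductal systolic and end-diastolic flow (6.1.2), the yes/no reversal item and peak systolic flow (6.3) and MRI ductal flow (6.1.3) are all planned at baseline and with MH. Scenario 1 describes the ductal response through peak systolic flow and end-diastolic reversal, and neither needs the ratio. This stands, and it limits the point to one derived variable.

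A reader might infer that the measure vanishes specifically in the non-responders the study wants to find. The documents do not support that. Section 2.4 is silent on ductal reversal in scenarios 2 to 4. Responders may also lack a value, at baseline. Absent end-diastolic reversal does not prove zero reverse flow over the whole cycle, and 6.3 lists the two as separate items.

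The ROC consequence is also conditional. Section 8 names no index variable and does not say that undefined values are excluded. At a single time point F/R = 1/f − 1, where f is the reverse fraction. The two therefore give the same ROC curve once absent reverse flow is ranked as the extreme, and near-zero instability does not matter there. It does matter for changes and for the paired plot.

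None of these arguments supplies a value for the ratio when reverse flow is zero.

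**Conclusion.** The point holds for this one index. The forward/reverse ratio is undefined at zero reverse flow, is unstable near it, and has no rule for either case. Because the plan ties reversal to the oxygen response, a complete-case paired or ROC analysis of the ratio would run on a subset plausibly selected by response, losing responders, non-responders or both.

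The size is not known. The half-widths of 0.169 to 0.271, against 0.147 with all 50, rest on assumed shares without reverse flow and an assumed AUC of 0.80. They show what could happen and are not a prediction. It would go too far to conclude that fetuses leave the study, that the ductal part of the primary objective cannot be assessed, or that this ratio is the deciding test. The change is worth making because the better index comes from the same Doppler traces and settles the scale before data are seen.

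**What to change.** In 6.1.2 and 6.3, replace the ratio with the reverse-flow fraction = reverse/(forward + reverse), using the same forward and reverse components of the Doppler trace that the ratio would need, and name those components. Record 0 when a readable trace shows no reverse flow, and a separate code for not obtained.

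In section 8, analyse the absolute change (MH minus baseline). A percent change would again be undefined when the baseline is 0. Keep every measured fetus in any ROC analysis of this index. Report the number with no reversal at each time point, alongside the existing yes/no item.

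The cost is a wording change and one replaced database field, or two if the components are stored. No extra imaging or oxygen time is needed. Section 6.3 does not now list the components, so they must be written down when the traces are measured offline.
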